11.0 Waiver of Consent/Authorization for Recruitment Purposes

This section is required when medical records may be reviewed to determine eligibility for recruitment.

11.1 * PRACTICABILITY OF OBTAINING CONSENT PRIOR TO ACCESS: Study personnel need to access protected health information (PHI) during the recruitment process and it is not practicable to obtain informed consent until potential subjects have been identified: (REQUIRED)

Yes

If **no**, a waiver of consent/authorization is NOT needed.

11.2 * RISK TO PRIVACY: A waiver for screening of health records to identify potential subjects poses no more than minimal risk to privacy for participants:

Yes

If **no**, a waiver of authorization can NOT be granted.

11.3 * RIGHTS/WELFARE: Screening health records prior to obtaining consent will not adversely affect subjects' rights and welfare:

Yes

If **no**, a waiver of authorization can NOT be granted.

11.4 * IDENTIFIERS: Check all the identifiers that will be collected prior to obtaining informed consent:

- Names
- Dates
- Postal addresses
- Phone numbers
- Fax numbers
- Email addresses
- Social Security Numbers*
- Medical record numbers
- Health plan numbers
- Account numbers
- License or certificate numbers
- Vehicle ID numbers
- Device identifiers or serial numbers
- Web URLs
- IP address numbers
- Biometric identifiers
- Facial photos or other identifiable images
- Any other unique identifier
- None

Note: HIPAA rules require that you collect the minimum necessary.

11.5 * HEALTH INFORMATION: Describe any health information that will be collected prior to obtaining informed consent:

All study investigators have access to the surgery schedule at the UCSF Mission Bay. Patient that are potential research participants (scheduled for surgeries with pre-existing ERAS pathways) will be identified. Research members will then collect the patient's name, medical record number, date of surgery. The patient's medical record will then be reviewed to screen for inclusion and exclusion criteria. If the patient is a potential candidate for enrollment, based on our inclusion/noninclusion criteria, will will retrieve the contact information to contact the patient.

Note: HIPAA requires that you collect the minimum necessary.

11.6 * DATA RETENTION/DESTRUCTION PLAN: Describe your plan to destroy any identifiable data collected to determine eligibility for recruitment. This should be done at the earliest opportunity. If you plan to retain identifiable recruitment data, provide the justification for doing so:

All identifying information will be destroyed at the earliest opportunity upon completion of the study.

12.0 Risks and Benefits

12.1 RESEARCH-RELATED RISKS: Check if your study involves any of these specific research-related risks

to participants that may need to be disclosed in the consent form:

- For interventional studies, risk that the regimen may be more harmful or less effective than other available interventions
- Risks associated with radiation exposure for imaging studies specifically for research purposes
- Risks associated with the administration of contrast agent for imaging studies
- Risks associated with withholding of treatment or discontinuation of current treatment (e.g., washout period is required by the study protocol)
- For randomized, placebo-controlled trials, possible temporary or permanent health consequences from the deprivation of effective therapies during the placebo administration period
- For studies involving a sham surgical procedure, the risk that participants may experience increased morbidity without the possibility of benefit
- Risks associated with modification or extension of a surgical procedure primarily for research purposes (e.g. risks associated with prolonging anesthesia, time in the operating room, etc.)
- Risk of pain or physical discomfort caused by the research intervention
- Possible personal discomfort due to sensitive topics (stress, embarrassment, trauma)

* For any boxes checked above, describe how you will minimize these risks and discomforts, e.g., adding or increasing the frequency of monitoring, additional screening to identify and exclude people with diminished kidney or liver function, or modification of procedures such as changing imaging studies to avoid giving contrast agent to people who are more likely to suffer side effects from it, etc.:

(REQUIRED)

Participants in the study have the risk that their study intervention (local anesthetic administration by bolus application or continuous infusion) results in inferior pain control. To ameliorate this risk we are firstly offering all patients the ability to obtain additional (demand) bolus administrations of local anesthetic and fentanyl through their epidural catheter. Secondly, all patients will have additional analgesics ordered in case they require additional pain control. We expect that all patients will be offered excellent pain control. For this reason, we did not choose pain scores as primary endpoint (we don't expect any differences here), but the need to administer additional analgesics.

12.2 RISKS: Describe any anticipated risks and discomforts not listed above:

There are risks associated with the placement and use of epidural anesthesia. However, this study will only be performed in patients who have already consented to the current standard of care in the ERAS pathways. ERAS pathways routinely include the use of epidural anesthesia. Patients in this study will be seen daily by the study investigators as well as the acute pain service at Mission Bay. They will routinely be asked for side effects of regional anesthesia such as hypotension, itching and the catheter site will be inspected. In case of hypotension with a mean arterial blood pressure <60 mmHg, nursing orders to contact the primary service and the acute pain service for appropriate clinical response remain in place.

12.3

MINIMIZING RISKS: Describe the steps you have taken to minimize the risks/discomforts to subjects. Examples include:

- **designing the study to make use of procedures involving less risk when appropriate**
- **minimizing study procedures by taking advantage of clinical procedures conducted on the study participants**
- **mitigating risks by planning special monitoring or conducting supportive interventions for the study**
- **having a plan for evaluation and possible referral of subjects who report suicidal ideation**

There will be no interference with the care of the patient. The treatment of enrolled patients is not different from patients who do not participate in the study. We have already been using the programmed intermittent bolus function successfully in these patients, but it always happened at the discretion of the ordering anesthesia provider.

All procedures will be performed by or under direct supervision of an anesthesiologist attending as per current institutional protocol. Medication changes to the epidural solution will be handled by physicians only as per current institutional protocol.

Patient data remains confidential and de-identified. Only encrypted computers will be used for data collection and management.

12.4 RESOURCES: Describe the resources in place to conduct this study in a way that assures protection of the rights and welfare of participants: These resources typically include appropriately trained and qualified personnel (in terms availability, number, expertise and experience), funding, space, equipment, and time to devote to study activities. Depending on the nature of the research study, investigators should consider the proximity or availability of critical resources that may be essential to the safety and welfare of participants, such as

- **the proximity of an emergency facility for care of participant injury**
- **availability of psychological support after participation**
- **resources for participant communication, such as language translation services**

The treatment of study patients does not deviate from our current clinical practice. The additional risks to the welfare of the patients should be minimal.
The use of a study coordinator facilitates patient enrollment and should minimize delays in the clinical care of the patients. All procedures the patients are undergoing are part of their regular medical care. The only additional study interventions are the programming of the pump, the follow visits and the follow up interview.
To protect the patient's privacy and medical information, all study documentation will be secured in a locked file cabinet. Data will be collected using RedCap. Only encrypted computer will be used.

12.5 * BENEFITS: (REQUIRED) Note: These are the benefits that the IRB will consider during their review. They are not necessarily appropriate to include in the consent form.

Possible immediate and/or direct benefits to participants and society at large (check all that apply):

- Positive health outcome (e.g. improvement of condition, relief of pain, increased mobility, etc.)
- Closer follow-up than standard care may lead to improved outcomes or patient engagement
- Health and lifestyle changes may occur as a result of participation
- Knowledge may be gained about their health and health conditions
- Feeling of contribution to knowledge in the health or social sciences field
- The research presents a reasonable opportunity to further the understanding, prevention, or alleviation of a serious problem affecting the health or welfare of children
- Other benefit (describe below)
- None

12.6 RISK TO BENEFIT RATIO: Explain why the risks to subjects are reasonable in relation to anticipated benefits, if any, to the participant or society:

The treatment of study patients does not deviate from our current clinical practice. The additional risks to the welfare of the patients should be minimal.

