4.0 Initial Screening Questions - Updated 2015

(Note: You must answer every question on this page to proceed.)

4.1 * PROJECT SUMMARY: (REQUIRED) Give a brief overview of this project (250 words or less). Tell us what this study is about, who is being studied, and what it aims to achieve. If you have an NIH Abstract, paste it here: Click on the orange question mark to the right for more detailed instructions.

Epidurals are an effective means for providing neuraxial anesthesia and analgesia. Prior studies in labor epidurals have demonstrated that a programmed intermittent bolus application of local anesthesia can improve pain control thus reducing the amount of local anesthetic required as well as improve patient

satisfaction when compared to continuous epidural infusions. The effects of programmed intermittent bolus of epidurals compared to continuous epidural infusions in a surgical setting have yet to be elucidated. Our goal is to evaluate the use of programmed intermittent bolus compared to continuous epidural infusion in a surgical patient population. We plan to enroll patients already undergoing surgery under the enhanced recovery after surgery (ERAS) pathways. ERAS pathway surgeries include colorectal, gynecologic, surgical oncology to name a few. The primary endpoints of the study will be the total local anesthetic consumption and total opioid consumption as surrogate markers for the quality of epidural anesthesia. Secondary endpoints are pain scores and functional measurements, patient satisfaction, and incidence of hypotension .

4.2 * HUD DEVICE: (REQUIRED) Does this application involve a Humanitarian Use Device (HUD):

- No
- Yes, and it includes a research component
- Yes, and it involves clinical care ONLY

4.3 * TYPE OF RESEARCH: (Click the Help link for definitions and guidance): (REQUIRED)

- Biomedical research
- Social, behavioral, educational, and/or public policy research
- Hybrid - includes aspects of BOTH types of research (check this option if your research is mainly social /behavioral but also involves specimen collection or blood draws to look at biological measures)

4.4 * SUBJECT CONTACT: (REQUIRED) Does this study involve ANY contact or interactions with participants:

- Yes (including phone, email or web contact)
- No (limited to medical records review, biological specimen analysis, and/or data analysis)

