7.0 Research Plan and Procedures

7.1 This new consolidated section requests information about:

- Hypothesis
- Aims
- Study Design
- Background and Significance
- Preliminary Studies
- Procedures
- Statistical Methods
- References

Later sections include:

- Drugs and Devices
- Sample Size, Eligibility, and Subjects
- Recruitment and Consent
- Risks and Benefits
- Data and Safety Monitoring Plan
- Confidentiality, Privacy and Security
- Financial Considerations
- Qualifications of Personnel
- Other Approval and Registrations

7.2 HYPOTHESIS: Describe the hypothesis or what the study hopes to prove (Help Text updated 9/13):

Null hypothesis: There is no difference in total local anesthetic and opioids required when comparing patients receiving epidural anesthesia using either programmed intermittent epidural boluses or continuous epidural infusions following abdominal surgery.

7.3 AIMS: List the specific aims:

The aim of this study is to prove the superior efficacy of programmed intermittent bolus administration of epidural medications compared to traditional continuous infusions in providing adequate post-operative analgesia and patient satisfaction in a surgical patient population.

7.4 DESIGN: Briefly describe the study design (e.g., observational, interventional, randomized, placebo-controlled, blinded, cross-over, cross-sectional, longitudinal, pharmacokinetic, etc.):

This is a prospective, randomized controlled study of programmed intermittent bolus administration of local anesthetic in epidural anesthesia compared to traditional continuous infusions for patients undergoing surgery as part of the enhanced recovery after surgery pathway.

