As part of the UCSF Enhanced Recovery After Surgery (ERAS) pathway, all patients routinely treated with thoracic/lumbar epidural anesthesia for post-operative analgesia. The planned investigation does not change its approach, but compares solely two different modalities how epidural medications are administered. The study ends when the catheters are removed which is most often on post-operative day two, but can be later in case the patient may still benefit from epidural anesthesia. During the duration of the treatment with epidural anesthesia, enrolled patients will be randomized to receive either programmed intermittent bolus or continuous epidural administration of the local anesthetic ropivacaine (0.0625%) with fentanyl (2ug/ml). In addition to this maintenance administration of local anesthetic, the patient are also able to apply additional (demand) boluses of epidural medication by pressing a button. This technique, called patient- controlled epidural anesthesia (PCEA), is routinely used in all patients with epidural catheters and allows patients to receive additional medication in the event they experience discomfort. If the patients have still pain not covered by epidural anesthesia, they have access to additional RN-administered opioid pain medication. The normally used drugs for such treatment are oxycodone p.o. and hydromorphone i.v. However, other opioids could be used in this context and all opioid use would be quantified using a conversion to oral morphine equivalents. The primary outcomes of the study will be the total amount of local anesthetic administered and opioid requirements (oral morphine equivalents). Secondary outcomes are: numeric pain rating scores (should not be different as patients have access to additional analgesic medication), number of patient attempts to trigger additional PCEA boluses, overall patient satisfaction assessed through validated questionnaires, and incidence of hypotension.

7.5 BACKGROUND AND SIGNIFICANCE: Briefly provide the background and significance of this study (e.g. why is this study needed) (space limit: one half page):

If this is a first in humans study, please summarize the safety data from the animal studies. For pediatric drug or device studies, please identify if this is the first study in pediatric populations.

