7.9 * PROCEDURES / METHODS: (REQUIRED)

For clinical research, list all study procedures, tests and treatments required for this study, including when and how often they will be performed. If there are no clinical procedures, describe the research activities.

If some of the activities would occur even if the person were not in the study, as in the case of treatment or tests performed for diagnostic purposes, clearly differentiate between those activities that will be done solely for research purposes and those that are happening as part of routine care.

Examples may include:

- additional scans outside standard clinical diagnosis or monitoring
- additional biopsies to collect tissue for research
- extra clinic visits
- extra lab tests not required for clinical care

If you have a procedure table, attach it to the submission with your other study documents.

All study participants will complete a questionnaire that includes their pain history, an anxiety and depression questionnaire (Hospital Anxiety and Depression Scale) and the WHO Disability Assessment Schedule 2.0 (WHODAS 2.0). Patients will be block randomized to the programmed intermittent bolus group or continuous infusion group. As part of the existing ERAS pathways, all patients will receive a thoracic/lumbar epidural catheter prior to their scheduled surgical procedure depending on the anticipated surgical incision site. Both groups will receive the same standard concentration of local anesthetic (0.0625% ropivacaine) and opioid (fentanyl 2ug/mL) based epidural mix. A total of 8mL of the epidural mix will be administered every hour either as a continuous infusion (8mL/hr) or programmed intermittent epidural bolus (4mL bolus every 30 min) based on the study participant's randomization. The epidural will be started in the OR, prior to the end of the surgical procedure at the discretion of the intraoperative anesthesia provider.

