The clinical investigator who enrolled the patient will write the epidural infusion orders. A PACU nurse will be programming the pump following hospital policies. The attending in the acute pain service will be informed about the enrollment of the patient in the study to ensure the pain service has all the information needed to ensure the best pain control to the patient in accordance with the study protocol. The display of the pump will be covered with a removable cover to make sure that the patient will stay blinded about the treatment group. The epidural pumps will subsequently be managed by the acute pain service, not the study investigators. The study protocol allows the reduction of epidural flow rates from 8ml to 6ml/h (from 4ml q30 to 3 ml q30 min in the bolus group) in case of hypotension.

Patients will have the option to administer patient controlled epidural analgesia (PCEA) in addition to the basal rate. For continuous epidural infusion group, they can receive additional 2ml every 15 minutes (lock out period) for a total of 16ml/hr (8ml/hr from continuous infusion and up to 8ml from PCEA). To match the total epidural volume in the programmed intermittent bolus group, they can receive additional 2ml

using a lock out period of 10 minutes. Because 4ml of epidural is bolused every 30 min and a PCEA bolus cannot coincide with the basal bolus doses, the shortend lock out period is necessary to make sure the patient can still receive the same four additional 2ml PCEA boluses as the continuous infusion group.

In addition, patients will be able to receive additional physician manual boluses, IV opioid medications from nursing staff, adjunct medications as per standard UCSF ERAS protocol. Hypotension and itching are some common adverse reactions to epidural analgesia; we will treat and document these episodes as per preexisting UCSF acute pain service epidural protocol.

Outcome measures will be total local anesthetic use (charted by nursing staff each shift as part of routine care), numeric rating scale (charted by nursing staff as part of routine care), total PCEA button presses (recorded on epidural pump), anxiety and functional measures (WHODAS2.0, brief pain inventory, HADS survey) to be measured on post operative day 1 and 2. Incidence of hypotension (charted by nursing staff as part of routine care).

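### The primary outcome is worded differently across sections, and total local anesthetic is not divided by epidural hours although the trial is sized on dose per hour

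*Combined protocol and SAP*

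**What the plan says.** Five places in the combined protocol and SAP bear on the primary outcome.

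- **4.1 (project summary):** "The primary endpoints of the study will be the total local anesthetic consumption and total opioid consumption".
- **7.2 and 7.4 (hypothesis, design):** the null hypothesis covers the same pair, "There is no difference in total local anesthetic and opioids required", and the design section repeats it: "The primary outcomes of the study will be the total amount of local anesthetic administered and opioid requirements (oral morphine equivalents".
- **7.9 (procedures):** the list begins "Outcome measures will be total local anesthetic use (charted by nursing staff each shift as part of routine care), numeric rating scale" and goes on to button presses, functional and anxiety measures and hypotension. It contains no opioid outcome and marks nothing as primary.
- **9.3 (sample size):** the justification compares local anesthetic dose per hour of analgesia, 10.5 against 12.3 mg/h, and carries over a standardized effect of 0.6.
- **12.1 (research-related risks):** "we did not choose pain scores as primary endpoint (we don't expect any differences here), but the need to administer additional analgesics".

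On dosing, 7.9 states: "A total of 8mL of the epidural mix will be administered every hour either as a continuous infusion (8mL/hr", or the same hourly volume as programmed boluses. The rate may be lowered to 6 mL/h for hypotension. The epidural is started in the operating room when the anesthesia provider chooses (7.9). Removal is usually on postoperative day 2, but may be later (7.4) or earlier (10.13).

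**The concern.** There are two problems.

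First, the wording. A total that includes basal drug, a dose per hour, and a need for extra analgesics are three different variables. Section 7.25 names only generic tests and no primary analysis, and 13.2 plans a look at outcomes after 44 patients. Unless the sections are reconciled, the definition could be settled after data have been seen.

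Second, time. Neither 4.1 nor 7.4 divides the total by epidural hours or fixes an observation window. Every extra hour of epidural adds basal drug whatever the patient needed. If duration varies much, the total carries noise unrelated to the quality of the block, and the 44 per group calculated for a per-hour variable no longer gives the planned power.

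**Working it through.** **1. The plan's own figure.** Two-sided alpha 0.05, power 80%, effect 0.6:

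n = 2 × (1.960 + 0.842)² / 0.6² = 43.6, so 44 per group. This reproduces 9.3. With the t distribution, 44 per group gives 79.5% power. The calculation belongs to mg per hour, the variable quoted in 9.3.

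**2. Doses from 7.9.** 0.0625% is 0.625 mg/mL.
- Basal: 8 mL/h × 0.625 = 5.0 mg/h. Reduced: 6 × 0.625 = 3.75 mg/h.
- One PCEA bolus: 2 mL × 0.625 = 1.25 mg.
- Six more hours of basal: 30 mg, or 24 PCEA boluses.

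**3. What duration does to a total.** Take one patient with 48 h and no demand bolus, and another with 40 h and 24 boluses.
- Total: 48 × 5 = 240 mg against 40 × 5 + 24 × 1.25 = 230 mg. The patient who needed more scores lower.
- Per hour: 240/48 = 5.00 against 230/40 = 5.75 mg/h. The order is now right.

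**4. Size of the power loss.** The documents give no demand rate and no spread of duration, so these are assumptions: demand 1.25 mg/h with SD 0.75 in the infusion arm; a reduction of 0.6 × 0.75 = 0.45 mg/h in the bolus arm; constant basal; duration with mean 42 h and SD 3, 6 or 9 h, independent of demand and the same in both arms; 44 per group; two-sided t-test.

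Mean rates are 6.25 and 5.80 mg/h, and the difference in totals is 0.45 × 42 = 18.9 mg. For a rate with mean m and SD 0.75 multiplied by hours with SD s:

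Var(total) = 42² × 0.75² + s² × m² + s² × 0.75²

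For s = 6 and m = 6.25 this is 992.25 + 1406.25 + 20.25 = 2418.75, an SD of 49.2 mg. For m = 5.80 the SD is 47.2 mg.

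| Duration SD | Pooled SD of total (mg) | Effect on total | Power, total mg (simulated) | Power, mg/h (simulated) |
|---|---|---|---|---|
| 3 h | 36.4 | 18.9/36.4 = 0.52 | 67% | about 79% |
| 6 h | 48.2 | 18.9/48.2 = 0.39 | 45% | about 79% |
| 9 h | 63.1 | 18.9/63.1 = 0.30 | 29% | about 79% |

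The simulation used gamma-distributed demand rates and normal hours. Power computed from the effect sizes in the third column agrees within about one percentage point.

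**5. Does the basal dose itself cost power?** Total mg/h and demand mg/h both give 78–80%. Adding a constant 5 mg/h to every patient changes neither the difference in means nor the SD. It matters only when rates are reduced. If an assumed 20% of each arm ran at 3.75 mg/h throughout, the variance of the rate becomes 0.75² + 0.2 × 0.8 × 1.25² = 0.8125 (SD 0.90), the effect is 0.45/0.90 = 0.50, and power on total mg/h is about 64%, against 79% on demand mg/h.

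**The case against.** The strongest reply is that 4.1, 7.2 and 7.4 were written to state the endpoints and agree with each other, while 12.1 is a risk answer explaining why pain scores were not chosen. Much of this stands, and it rules out four stronger readings that a reader might infer.

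- **That the trial tests a different variable from the one it chose.** Opioid use is itself a primary in 4.1, 7.2 and 7.4, and rescue opioid is a main form of additional analgesic, so 12.1 overlaps with half of the pair.
- **That opioid use will not be measured.** The 7.9 list is incomplete, but 7.4 says "all opioid use would be quantified using a conversion to oral morphine equivalents", and 10.13 takes adjunct analgesic amounts from the chart.
- **That the basal dose swamps the effect.** A constant basal dose cancels (step 5). The loss comes from not dividing by hours.
- **That 12.1 makes demand dose the primary.** It offers demand boluses as the first safeguard and then adds "Secondly, all patients will have additional analgesics ordered in case they require additional pain control". Read narrowly, its endpoint excludes PCEA. A demand-dose primary would also lean on lockouts that differ by arm (15 and 10 minutes) and would ignore basal reductions.

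It is also fair to say that 9.3 already thinks in mg per hour, so the authors may intend that variable. But 4.1, 7.2 and 7.4 do not say so, and that is the gap.

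**Conclusion.** The point holds as a mismatch of definitions with one consequence for the analysis. Sections 4.1, 7.2 and 7.4 agree on two primaries; 12.1 paraphrases them loosely, 7.9 drops one, and 9.3 sizes the trial on a per-hour form of the other. As worded, total local anesthetic depends on how long the epidural ran.

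Under the stated assumptions, power falls from about 79% for mg per hour to about 67%, 45% or 29% for total mg. The direction follows from the dosing scheme and the variable duration. The size depends on the assumed demand rate, its SD and the spread of hours, none of which the documents give, and on duration being unrelated to demand. That basal drug is part of the total is inferred from the word total; 4.1 and 7.4 do not spell it out. The documents do not support making demand dose the primary in place of the total; that is a trade-off.

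**What to change.** Before any outcome data are seen, including at the 44-patient interim look:

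1. Define the local anesthetic primary as mg per hour of epidural, the variable in 9.3, and state how start and stop are defined.
2. Keep rescue opioid, in oral morphine equivalents, as the other primary.
3. Use this wording in 4.1, 7.2, 7.4, 7.9 (adding the opioid outcome) and 12.1.
4. Report demand dose (PCEA plus manual boluses, mg/h) as a secondary or sensitivity outcome, because basal reductions for hypotension lower the total for reasons unrelated to need.

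The cost is a wording amendment and more detailed data capture: start and stop times for each epidural, and delivered basal volume recorded separately from demand volume. Section 7.9 currently provides only shift-level charting of total use and a pump count of button presses. No change to treatment or sample size is needed for this point.
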